7.3 Laboratory Data Flow

The DMCC will provide the study with a specimen database that allows tracking of the collection, storage, and transfer of biological specimens, their submission to laboratories for testing, and the incorporation of laboratory results in the study database.

7.4 Study Records Retention

Patient files and other source data shall be kept for the maximum period of time to meet

all regulatory requirements, including those of the hospital or institution.

Additional requirements for record retention are those required by the Food and Drug Administration for studies conducted under IND. The investigator shall retain records required to be maintained under this part for a period of 2 years following the date a marketing application is approved for the drug for the indication for which it is being investigated; or, if no application is to be filed or if the application is not approved for such indication, until 2 years after the investigation is discontinued and FDA is notified.

To fulfill requirements of the National Institutes of Health, grantees must retain the records pertinent to all studies supported by the award for three years from the date the final Federal Financial Report is submitted to NIH.

7.5 Protocol Deviations

The following protocol deviations will be recorded and summarized in the final report:

- 1) eligibility (inclusion/exclusion) violations,
- 2) study drug dosing violations,
- 3) excluded medication violations,
- 4) procedures performed outside the protocol-specified window,
- 5) procedures not done,
- 6) subject non-compliance and
- 7) other, to be specified by the Investigator.

8. Human Subjects

8.1 GCP Statement

This clinical trial will be conducted in accordance with the ethical principles that have their origin in the Declaration of Helsinki, and that are consistent with Good Clinical Practice and all applicable regulatory requirements.

8.2 Benefits

The potential benefits of this study are: Severe osteogenesis imperfecta is both debilitating and progressive, and, as discussed previously, treatment options for adults with severe OI are limited. This work will have a direct impact on the treatment of these patients if it is found that therapy to decrease TGF β activity in humans with severe OI is safe and has beneficial effects on bone as assessed by biochemical markers and a BMD. If successful, such therapy may be of significant benefit in reducing the fracture rates and pain, and improving the quality of life of individual study participants. In addition, participants will have access to routine medical care and follow-up.

Severe osteogenesis imperfecta not only takes its toll on individuals who have the disease, but it also impacts society as a whole through the devastating loss of human potential resulting from the disorder. In addition, medical care for a person with type III or IV OI requires a variety of interventions, many of which are expensive and place an increased burden on our already overextended health care system. This phase I clinical trial should provide important information about a possible new therapy for patients with OI. If successful, such therapy may be of significant benefit in reducing the morbidity and improving the quality of life in these patients. As well as reducing the suffering of

those with the most severe forms of OI, a beneficial therapy might decrease the frequency of medical interventions now required to manage the disease. No matter what the outcome of the trial, the information to be learned could be useful in optimizing therapy and clinical management of patients with this disorder.

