3.2 Current Therapies Available

The current medical therapy for OI is limited to medications that are FDA-approved for treatment of osteoporosis. Bisphosphonates (BPNs), a class of antiresorptive medications, are generally considered as standard of care. The rationale for BPN therapy in OI is that this could increase the bone mineral density, and the increased bone mass albeit with abnormal matrix could potentially reduce fracture rates. Bisphosphonates increase bone mineral density in children and adults with OI; however, their efficacy in reducing fractures is still unclear, particularly in adult patients.^{10,11} More recently, human and murine studies have raised concerns that long-term use of BPNs in OI could result in impaired bone quality and adverse effects such as atypical fractures.¹²⁻¹⁴ An alternative approach to increase bone density and bone quality is the use of bone anabolic agents. A recent trial with teriparatide, a

bone anabolic agent approved for treatment of osteoporosis, showed that efficacy of such therapy is rather limited in those who need therapy the most, i.e., individuals with moderate-to-severe OI.¹⁵ Thus, the current strategy of repurposing approved anti-osteoporotic medications for OI has significant limitations as these do not target the primary pathogenetic mechanisms involved in the causation of bone fragility. Additionally, none of the current therapies are geared towards treatment of extraskeletal manifestations such as pulmonary disease. Currently, there are no disease-specific therapies for OI, and availability of such modalities would be of significant importance to patients.

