4.1 Inclusion Criteria (Stage 1 and Stage 2)

1. Willing and able to provide signed informed consent.
2. Age \geq 18 years
3. Diagnosis of moderate-to-severe OI based on history of more than 20 fractures in lifetime.
4. Glycine substitution in *COL1A1* or *COL1A2*, or pathogenic variants in *CRTAP*, *PPIB*, or *LEPRE1* (if genetic information is unavailable at screening, this may be assessed at screening visit on a clinical or research basis).
5. Females of child-bearing potential must have a negative urine pregnancy test, agree to and have the ability to use acceptable birth control method for entire duration of the study.
6. Males who enroll in the study and their partners must agree to use an acceptable form of birth control for the entire duration of the study.

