5.10 Quality Control: Study Related Procedures

Accurate, consistent and reliable data will be ensured through the use of standard practices and procedures. The DMCC will audit the Investigators' source data against eCRF entries and verify that the data are accurate.

6. Statistical Considerations

This study is designed to assess the safety and tolerability of fresolimumab in patients with Osteogenesis Imperfecta.

Sample Size: No formal sample size calculations were done for this study. The sample size was selected to allow for an initial assessment of safety in this population and dose range and feasibility of enrollment in this rare disorder. The sample size is 8 for the single dose study and 8 for the repeat dose study. The overall enrollment will be 16.

If needed, 2 additional patients will be enrolled in the repeat dose study to account for a drop-out rate of 20%.

Treatment-Related Adverse Events will be summarized by dose groups. Changes in vital signs, EKG, shifts in laboratory assessments and physical examinations, and patient-reported symptoms will be described. These will assess the primary endpoint of safety. Percent change in bone remodeling markers will be analyzed using a mixed model. BMD in the lumbar spine and the hip at 6 months for single dose study and 12 months for the multiple dose study will be compared to pretreatment levels using a Wilcoxon Signed Rank test. Percent change in the variables of the pulmonary function tests, and change in the 6-minute walk tests, and Numeric Rating Scale (NRS) for pain will be evaluated by Wilcoxon Signed Rank test. Values for derived pharmacokinetic variables, including Cmax, area under the curve, distribution, half-life (T1/2a), elimination half-life (T1/2b), clearance (CL), and volume of distribution at steady state (Vss), will be calculated as previously described and summarized by dose-group using descriptive statistics.

7. Data Management

The results from Screening and data collected during the study will be recorded in the

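### Section 6 summarises only treatment-related adverse events and counts no on-study fractures, so fractures attributed to OI can be missing from the planned safety summary

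*Combined protocol and SAP*

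**What the plan says.** **Population and drug.** Section 4.1 requires "Diagnosis of moderate-to-severe OI based on history of more than 20 fractures in lifetime". Section 3.5 states that the drug's effects on bone turnover and bone mass are so far unstudied. Section 3.2 notes that bisphosphonates raise bone mineral density (BMD) in OI but that "their efficacy in reducing fractures is still unclear, particularly in adult patients".

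**Hoped-for benefit.** Section 8.2 foresees an impact on treatment if the therapy proves safe and "has beneficial effects on bone as assessed by biochemical markers and a BMD". It adds, conditionally, that "such therapy may be of significant benefit in reducing the fracture rates and pain, and improving the quality of life of individual study participants".

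**Outcomes.** The Synopsis and Sections 4.7 and 4.8 make adverse events and serious adverse events a primary outcome in both stages, with no limit by attribution. The other primary items are vital signs, laboratory values and EKG, plus pharmacokinetics in Stage 1. Secondary outcomes are bone markers and BMD. Stage 2 adds forearm pQCT, pain, lung function, quality of life and the walk test. Fracture is in neither list.

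**Analysis.** The only adverse-event summary planned in Section 6 is of treatment-related events, by dose group. Vital signs, EKG, laboratory shifts, examinations and patient-reported symptoms are to be described. Of this set the plan says: "These will assess the primary endpoint of safety".

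**Monitoring.** Under Section 5.1 the DSMB reviews adverse events of every kind every 6 months. The Grade 4 criteria in Sections 5.7 and 5.8 leave out events that stem directly from the skeletal complications of OI.

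**The concern.** Fracture defines this disease, and TGFβ inhibition is expected to act on bone. A change in fracture frequency, in either direction, is an obvious thing to look for in a first safety study in this population.

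In people who have each had more than 20 fractures, the natural attribution of a new one is to OI. An adverse-event summary restricted to treatment-related events is therefore most likely to drop the events that bear most directly on bone safety. In an uncontrolled trial the investigator cannot tell a disease fracture from a drug-influenced one, so attribution is a poor filter here.

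At stake is the completeness of the safety report. A reader of the planned summary could not tell whether there were no fractures or several that were judged unrelated.

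**Working it through.** **1. The plan's own sample-size figure.** Section 6 states "The sample size is 8 for the single dose study and 8 for the repeat dose study", and "If needed, 2 additional patients will be enrolled in the repeat dose study to account for a drop-out rate of 20" percent. Check: 8 / (1 − 0.20) = 10, so 2 extra. It reproduces, and the point does not depend on it. There is no power or alpha to reproduce: "No formal sample size calculations were done for this study".

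**2. Following one on-study fracture through the plan.**

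| Step | Where | Is the fracture counted? |
|---|---|---|
| Outcome list | Synopsis, 4.7, 4.8 | Only as an unnamed adverse event |
| Follow-up visit procedures | 4.7, 4.8, 4.10 | No fracture item; skeletal survey at screening only |
| Adverse-event note under the schedule | 4.10 | Bleeding, edema, hematomas, gingival hyperplasia, blood in urine; not fracture |
| DSMB review | 5.1 | Yes, if recorded |
| Grade 4 criteria | 5.7, 5.8 | No, if due to skeletal complications of OI |
| Planned adverse-event summary | 6 | No, if judged unrelated to treatment |

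Elsewhere fracture serves only for eligibility and rescreening, the recent-fracture check on Day 1, and the choice of forearm for pQCT.

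**3. Exposure.** Stage 1: 8 × 0.5 year = 4 person-years. Stage 2: 8 × 1 year = 8. Total 12, or 2 per Stage 1 group (4 × 0.5) and 4 per Stage 2 group (4 × 1). This assumes complete follow-up and no use of the 2 extra places.

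**4. Expected number (assumed rates).** The documents give no fracture rate. Spreading 20 fractures over 60 or 18 years gives 20/60 = 0.33 and 20/18 = 1.1 per person-year; 0.1 is added as a low value for adulthood.

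- 12 × 0.1 = 1.2
- 12 × 0.33 = 4.0
- 12 × 1.1 = 13.2

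The Poisson chance of at least one fracture is 1 − exp(−1.2) = 70% at the lowest rate and 1 − exp(−4.0) = 98% at the middle one. The criterion is more than 20 fractures, so 20 divided by age is a floor for the lifetime average and 1.1 is not a true upper limit. Adult rates may be lower than lifetime averages.

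**5. What a count could show.** The exact Poisson 95% interval for x fractures in T person-years is χ²(0.025; 2x)/(2T) to χ²(0.975; 2x+2)/(2T). In Stage 2 (T = 8):

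- 4 fractures: 0.50 per person-year, interval 0.14 to 1.28.
- 8 fractures: 1.0 per person-year, interval 0.43 to 1.97.

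Power to detect a change from an equally long pre-study window, by exact conditional binomial test at two-sided 0.05, with Poisson counts and no overdispersion:

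| Assumed baseline rate per person-year | 0.2 | 0.5 | 1 | 2 |
|---|---|---|---|---|
| Stage 2 (8), doubling | 3% | 13% | 30% | 59% |
| Stage 2 (8), halving | 0.3% | 5% | 13% | 30% |
| Both stages (12), doubling | 6% | 22% | 45% | 79% |
| Both stages (12), halving | 1% | 9% | 22% | 45% |

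Treating the pre-study rate as known without error would raise power for a doubling in Stage 2 to between 22% and 91% (one-sided 0.025), but the documents supply no such rate. Fractures clustering in some participants would lower all these figures.

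**The case against.** The strongest reply is that fractures are already covered. Adverse events are a primary outcome documented from Day 1 onward, the definition in Section 5.2 does not exclude fractures, the DSMB reviews all adverse events, and Section 5.5 has the DMCC post aggregate reports of all reported events. This stands as far as capture and oversight go. It does not reach the planned analysis, which is narrower than the outcome it is meant to serve. The examination findings and symptoms that Section 6 also describes might mention a fracture, but nothing there counts one. If the authors meant all events arising after treatment, Section 6 should say so.

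A second reply is that a phase 1 trial with four per group need not measure every hoped-for benefit. That also stands; this point asks for no fracture endpoint.

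Three stronger readings are tempting, and the documents do not support them.

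- A reader might infer that Section 8.2 would treat a BMD gain with more fractures as success. It requires the therapy to be safe as well. Its fracture statement is conditional and sits beside pain and quality of life, both measured in Stage 2. Rewording it would be a preference that changes no result.
- A reader might infer that the missing count is why the trial cannot show a change in fracture frequency. The power figures show that it would rarely do so even with a count.
- A reader might infer that adverse-event tables would collapse repeated fractures into one per participant. The documents state no such counting rule.

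**Conclusion.** The gap is real but narrow. Followed as written, the safety summary in Section 6 can omit every fracture attributed to OI, in a population defined by fractures and receiving a drug intended to change bone remodeling. Such fractures would still be open to DSMB review if recorded.

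The size is 12 planned person-years and, on assumed rates of 0.1 to 1.1 per person-year, about 1 to 13 fractures with no assured place in the planned summary. The exposure follows from the documents; the rates do not. The conclusion about Section 6 depends on neither.

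This is a worthwhile reporting improvement, not a flaw that threatens the trial's aims. Part of the drug-risk text in Section 5.3 was not available for this check and might mention bone effects, but it is not where outcomes or analyses are set. The discontinuation criteria are cited only to show where fractures are not counted; whether they are appropriate is not questioned here.

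**What to change.** Add to Section 6 a descriptive safety listing of every on-study fracture regardless of attribution: participant, site, date and days since last infusion. Add the count per person-year by stage and group, with exact Poisson intervals if wanted.

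Take the data from the adverse-event records kept from Day 1 onward, with a fracture prompt on the adverse-event form if site and date would not otherwise be captured. Medical history cannot be the source: the schedules place it at screening, and the visit text adds only Stage 1 Day 90.

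The cost is one listing and perhaps one form item, with no added procedure or visit. The downside is the risk of over-reading. With 12 person-years, four per group and no untreated arm, the counts are too few to test and must be labelled descriptive. Without follow-up skeletal imaging, the listing would hold only fractures that come to attention.

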8.3 Risks

The potential risks of this study are:

Blood samples will be drawn for safety labs. It is expected that there may be bruising and mild discomfort at the site of needle insertion when phlebotomy is performed. Fainting may even occur.

Participants will be exposed to radiation during dual-energy X-ray absorptiometry scanning and radiographs. The total amount of radiation that the participant will receive in this study is about 1.1 mSv or 110 mrem, and is approximately equivalent to a uniform whole body exposure of 133 days of exposure to natural background radiation. (Ref <http://www.doseinfo-radar.com/RADARDoseRiskCalc.html>). Though the biological effects of diagnostic radiation on humans have not been studied directly, the potential risk to an individual associated with techniques used for the assessment of bone status is believed to be very small since radiation doses are low. In 2012 the United Nations Scientific Committee on the Effects of Atomic Radiation stated that for typical background radiation levels (1–13 mSv per year), it is not possible to account for any health effects.

Patients may find the pulmonary function testing, function and mobility assessments and hearing tests to be tiring.

Protection from Risk: The study will be conducted in the Clinical and Translational Science Award (CTSA) Centers or research facilities of our respective institutions comprising the BBD Consortium whenever possible. When a CTSA/research facility is not available, study visits will be conducted in the investigator's clinic.

The study implementers will be nursing staff/coordinators of the Centers with a long experience in care of individuals with OI. If any participant should incur any unexpected and untoward event during the testing procedure, the emergency caregivers, would become available on an immediate basis to provide necessary emergent management.

Female participants will have no radiographic procedures while pregnant.

8.4 Written Informed Consent

Written informed consent will be obtained from each participant before any study-specific procedures or assessments are done and after the aims, methods, anticipated benefits, and potential hazards are explained. The participant's willingness to participate in the study will be documented in writing in a consent form, which will be signed by the participant with the date of that signature indicated. The investigator will keep the original consent forms and signed copies will be given to the participants. It will also be explained to the participants that they are free to refuse entry into the study and free to withdraw from the study at any time without prejudice to future treatment.

Written or oral information about the study in a language understandable by the participant will be given to all participants.

8.5 Process of Consent

Consent forms will be given to potential participants prior to enrollment so that they have ample time to review the information and ask questions about the study. Forms can be mailed to the individuals in advance of their participation so that can read and ask questions before considering participating. If participation is proposed during a clinic appointment, a copy of the consent form may be sent home with the patient along with study staff contact information. Potential enrollees will be encouraged to take their time in reviewing the consent, call with questions, and contact study staff if interested in enrolling.

Anytime consent is obtained, it is incumbent on the individual obtaining the consent to ascertain whether the potential participant and his/her legal representative understand all aspects of the study. Obtaining informed consent is an unhurried, interactive process with questions asked of both the Investigator and potential participant.

For non-English speaking subjects, a translator will be available to aid in the explanation of the protocol and consent and to answer questions. A short consent form in the subject's language will be used in addition to the full English consent form.

We will follow the usual consent procedures with those 18 years and over signing consent forms. All prospective participants will be asked to sign a medical records release form along with the study consent form. Medical records may be obtained to confirm OI diagnosis and affirm that none of the exclusionary conditions are present. Results from medical history and laboratory testing may be recorded.

